12.1.3 Exploratory outcome measures

- PD-L1 expression will be defined as the percentage of PD-L1 expression in the patients baseline tumour samples
- Cell free lymphoma DNA levels will be measured and correlated to the patients clinical disease status
- CyTOF study; putative biomarkers of response will be identified and immune cell changes will be correlated with any toxicity

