4.2 Exclusion Criteria

Patients are not eligible for the trial if they fulfill any of the following exclusion criteria:

- All patients with active CNS involvement of lymphoma
- Prior organ transplantation, including allogeneic stem-cell transplantation
- Significant acute or chronic infections including, among others:
 - Known history of testing positive test for human immunodeficiency virus (HIV) or known acquired immunodeficiency syndrome (AIDS),
 - Hepatitis B virus (HBV) or hepatitis C virus (HCV) infection at screening (positive HBV surface antigen or HCV RNA if anti-HCV antibody screening test positive)
- Current use of immunosuppressive medication, EXCEPT for the following:
 - intranasal, inhaled, topical steroids, or local steroid injection (e.g., intra-articular injection); Systemic corticosteroids at a maximum dose of $\leq 1 \text{ mg/kg}$ of prednisone or

equivalent during screening (to be stopped by day 1 of trial treatment); Steroids as premedication for hypersensitivity reactions (e.g., CT scan premedication).

- Active autoimmune disease that might deteriorate when receiving an immunostimulatory agent. Patients with diabetes type I, vitiligo, psoriasis, hypo- or hyperthyroid disease not requiring immunosuppressive treatment are eligible
- Known prior severe hypersensitivity to investigational product or any component in its formulations, including known severe hypersensitivity reactions to monoclonal antibodies (NCI CTCAE v4.03 Grade ≥ 3)
- Persisting toxicity related to prior therapy of Grade >1 NCI-CTCAE v 4.03; however, alopecia and sensory neuropathy Grade ≤ 2 or other Grade ≤ 2 not constituting a safety risk based on investigator's judgment are acceptable
- Pregnancy or lactation
- Known alcohol or drug abuse
- Clinically significant (i.e., active) cardiovascular disease: cerebral vascular accident/stroke (< 6 months prior to registration), myocardial infarction (< 6 months prior to registration), unstable angina, congestive heart failure (\geq New York Heart Association Classification Class II), or serious cardiac arrhythmia requiring medication.

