7.3 Assessments

Table 2. Schedule of Assessments

Parameter	Screening (28 days unless otherwise stated)	Cycle 1		Cycle 2		Cycle 3		Cycle 4		Cycle 5		Cycle 6		Cycle 7		Cycle 8		Subsequent cycles		End of Treatment /Progress ion	12 month Follow- up (from treatment start)	16 month Follow- up (from treatment start)	20 month Follow- up (from treatment start)
		Day 1	Day 15	Day 1	Day 15	Day 1	Day 15	Day 1	Day 15	Day 1	Day 15	Day 1	Day 15	Day 1	Day 15	Day 1	Day 15	Day 1	Day 15				
Informed consent	X																						
Medical History	X																						
Pregnancy test (if applicable)	X	X		X		X		X		X		X		X		X		X		X			
Prior Diagnosis/ Prior Treatment / baseline conditions	X																						
ECOG performance status	X	X		X		X		X		X		X		X		X		X		X			
Height (pre-study only)	X																						
Weight	X	X		X		X		X		X		X		X		X		X					
Diagnostic tissue biopsy (within 3 months of registration)	X																			X (optional)			
Bone Marrow Trehpine biopsy (within 3 months)	X																			X ¹			
Laboratory Tests (Haematology ² and Biochemistry ³)	X ⁴	X	X	X	X	X	X ⁴	X	X	X	X	X	X	X	X	X	X	X	X ⁴				
Virology (HIV, HBV, HCV)	X																						
Urinalysis (protein, glucose)	X	X		X		X		X		X		X		X		X		X		X			

Parameter	Screening (28 days unless otherwise stated)	Cycle 1		Cycle 2		Cycle 3		Cycle 4		Cycle 5		Cycle 6		Cycle 7		Cycle 8		Subsequent cycles		End of Treatment /Progression	12 month Follow-up (from treatment start)	16 month Follow-up (from treatment start)	20 month Follow-up (from treatment start)
		Day 1	Day 15	Day 1	Day 15	Day 1	Day 15	Day 1	Day 15	Day 1	Day 15	Day 1	Day 15	Day 1	Day 15	Day 1	Day 15	Day 1	Day 15				
and blood)																							
ACTH, Thyroid function (T4 & TSH), tests for pancreatitis		X				X				X					X					X			
ECG (single 12 lead)	X	X ⁵		X ⁵																X			
Clinical Disease assessment / physical exam	X	X		X		X		X		X		X		X		X		X		X	X	X	X
CT scans with IV contrast NCAP	X					X ⁶						X ⁶				X ⁶		X ⁷	X ⁸	X	X	X	X
Avelumab 10mg/kg every 2 weeks		X	X	X	X	X	X	X	X	X	X	X	X	X	X	X	X	X					
Concomitant Diseases and Treatment		<< Ongoing assessment until 28 days after treatment discontinuation >>																					
Adverse Events		<< Ongoing assessment until 28 days after treatment discontinuation >>																					
Blood samples collected for research	X				X				X				X				X		X ⁷	X	X	X	X

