7.4.2 Blood samples

Blood samples will be collected at baseline, day 15 cycle 2, day 15 cycle 4, day 15 cycle 6, day 15 cycle 8, at 12 months, 16 months and 20 months post treatment start (or equivalent time point if patient is off treatment). Plasma for cell free DNA studies will be collected and peripheral blood mononuclear cells will be isolated for a CyTOF immunophenotyping sub-study.

Samples will be processed as per the AVAIL-T laboratory manual and shipped to the University of Leicester in the shipment containers supplied by the trial.

We have established droplet digital (dd) PCR assays for some of the common mutations in PTCL - RHOAG17V, IDH2 and PLCG1. We plan to employ these assays on cell free DNA from patient plasma in order to explore their utility for diagnosis and as markers for response to treatment or predictors of relapse. We estimate that one or more of these genetic markers will be detectable in 25 to 40% of our patient population^{31,34-36}.

CyTOF is a cutting-edge technology that allows the measurement of an unprecedented number of T-cell markers on circulating T-cells. We plan to perform CyTOF analysis pre-treatment and after cycles 2, 4, and 6. These data will allow the characterisation of a relapsed/refractory PTCL signature, identify putative biomarkers of response, and correlate immune cell changes with any toxicity.

For further information please see the AVAIL-T sample collection manual.

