Grade 2 irAE or first occurrence of Grade 3 irAE	Withhold avelumab therapy 1.0 to 2.0 mg/kg/day prednisone or equivalent Add prophylactic antibiotics for opportunistic infections Specialty consult as appropriate	If improves to Grade \leq 1: Taper steroids over at least 1 month and resume avelumab therapy following steroids taper.
Recurrence of same Grade 3 irAEs	Permanently discontinue Avelumab therapy 1.0 to 2.0 mg/kg/day prednisone or equivalent Add prophylactic antibiotics for opportunistic infections Specialty consult as appropriate	If improves to Grade \leq 1: Taper steroids over at least 1 month
Grade 4	Permanently discontinue Avelumab therapy 1.0 to 2.0 mg/kg/day prednisone or equivalent Add prophylactic antibiotics for opportunistic infections Specialty consult as appropriate	If improves to Grade \leq 1: Taper steroids over at least 1 month
Requirement for 10 mg per day or greater prednisone or equivalent for more than 12 weeks for reasons other than hormonal replacement for adrenal insufficiency Persistent Grade 2 or 3 irAE lasting 12 weeks or longer	Permanently discontinue Avelumab therapy Specialty consult	

Abbreviations: ACTH=adrenocorticotropic hormone; ADL = activities of daily living; ALT = alanine aminotransferase; AST = aspartate aminotransferase; BNP=B-type natriuretic peptide; CK-MB=creatine kinase MB; CT = computed tomography; FSH=follicle-stimulating hormone; GH=growth hormone; IGF-1=insulin-like growth factor 1; irAE = immune-related adverse event; IV=intravenous; LH=luteinizing hormone; MRI = magnetic resonance imaging; NCI-CTCAE = National Cancer Institute-Common Terminology Criteria for Adverse Event; PRL=prolactin; T4 = thyroxine; TSH = thyroid-stimulating hormone; ULN = upper limit of normal.

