7.7 Concomitant Medication

Primary prophylactic use of granulocyte-colony stimulating factors is permitted during the study. They may also be used to treat treatment emergent neutropenia as indicated by local guidelines.

Use of erythropoietic growth factors is allowed during the study.

Patients are prohibited from receiving the following therapies during the treatment phase of this trial:

- Anti-cancer systemic chemotherapy or biological therapy
- Immunotherapy not specified in this protocol
- Investigational or experimental agents other than avelumab
- Radiation therapy (with the exception of Palliative radiotherapy to specific sites of disease considered medically necessary by the treating physician. All attempts should be made to rule out disease progression in the event of increased localized pain. If palliative radiotherapy is needed to control bone pain, the sites of bone disease should be present at baseline, otherwise, bone pain requiring radiotherapy will be considered as a sign of disease progression.).
- Immunosuppressive drugs, unless otherwise indicated for the treatment of AEs (see Tables 3 and 4). See below Clarification about Steroid Use.
- Any vaccine therapies for the prevention of infectious disease (eg, human papilloma virus vaccine) except for inactive vaccines (e.g. the flu vaccine).
- Herbal remedies with immune-stimulating properties (eg, mistletoe extract) or known to potentially interfere with major organ function (eg, hypericin).

Clarifications about Steroid Use: Data indicate that corticosteroids have an adverse effect on T cell function and that they inhibit and damage lymphocytes.

Therefore, the use of steroids during this trial is restricted as follows:

- Therapeutic use: for the treatment of infusion-related reactions and short-term treatment of AEs, steroids are permitted according to the modalities indicated in table 3 and 4
- Physiologic use: steroid replacement for adrenal insufficiency at doses equivalent to ≤ 10 mg prednisone daily is acceptable.
- Prophylactic use (eg, for the prevention of acute infusion-related reactions): is prohibited – unless otherwise indicated in Table 3

There are no prohibited therapies during the Post-Treatment Follow-up Phase.

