12.2 Analysis of Outcome Measures

Primary Outcome Measures

- Best overall response rate (PR + CR) during 8 cycles of treatment will be presented as the number and proportion of patients achieving a response over the total number of patients registered to the trial. Patients who die due to disease or toxicity during the first 8 cycles of treatment and patients who are not assessable will be classed as non-responders.

Posterior probability plots will also be produced together with the probability that the true effect is greater than 35%.

Secondary Outcome Measures

- Toxicity - The number and proportion of patients who experience one or more grade 3 or 4 adverse event or serious adverse event of any grade will be reported over the total number patients in the trial

- Time to event outcomes will be estimated using Kaplan Meier method. Point estimates will be presented at 6 and 12 months with 95% confidence intervals.
- Reduction in tumour size measured as maximum percentage change in the radiological sum of the product of the diameters from baseline will be presented as a mean and standard deviation or medians with an interquartile range depending on the distribution of the data.

Exploratory outcome measures

- Percentage of PD-L1 expression will be analyses at the Leicester Cancer Centre
- Cell free DNA levels and disease status correlation will be performed by the Leicester Cancer Centre
- Multicolour peripheral blood immunophenotyping will be performed by the Leicester Cancer Centre
- CyTOF study: biomarkers of response data will be acquired via mass flow cytometry at the Leicester Cancer Centre

All summaries and statistical analyses will be performed on an intention-to-treat (ITT) population including patients who are ineligible or non-compliant and a per protocol population of only patients who were eligible and received at least 1 dose of treatment.

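### The CyTOF baseline blood is drawn at screening, when systemic steroids are allowed, and the correlation of immune changes with toxicity has no rule on sample timing or steroid exposure

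*Combined protocol and SAP*

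**What the plan says.** All references are to the combined protocol and SAP.

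- **Purpose.** Section 12.1.3: "putative biomarkers of response will be identified and immune cell changes will be correlated with any toxicity". Section 7.4.2 also wants the data to characterise a disease signature.
- **Time points.** Section 7.4.2: "We plan to perform CyTOF analysis pre-treatment and after cycles 2, 4, and 6". The draws themselves: "Blood samples will be collected at baseline, day 15 cycle 2, day 15 cycle 4, day 15 cycle 6, day 15 cycle 8", then at 12, 16 and 20 months.
- **Visit of the baseline draw.** In Table 2 (section 7.3) the row "Blood samples collected for research" has its first mark under screening. Cycle 1 is blank, and the next mark is cycle 2 day 15. Section 5.1 lets screening assessments take place up to 28 days before registration.
- **Steroids at screening.** Section 4.2 accepts a maximum of 1 mg/kg of prednisone or "equivalent during screening (to be stopped by day 1 of trial treatment").
- **Steroids on treatment.** Section 7.7 allows them for infusion reactions and adverse events as set out in Tables 3 and 4. For a number of immune-related events Table 4 gives "1.0 to 2.0 mg/kg/day prednisone or equivalent" (prednisolone in some rows), then a taper of a month or more.
- **Why steroids matter.** Section 7.7: "Data indicate that corticosteroids have an adverse effect on T cell function and that they inhibit and damage lymphocytes".
- **Analysis.** Section 12.2 says only "CyTOF study: biomarkers of response data will be acquired via mass flow cytometry at the Leicester Cancer Centre". Sections 7.4.2, 12.1.3 and 12.2 contain no rule on steroid exposure at the draw, and none on whether a sample must precede the toxicity it is correlated with.

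**The concern.** The reference sample can be taken under a drug that the protocol says alters the cells being measured, and that drug must be stopped before avelumab starts. For those patients the change from baseline contains recovery from steroids. The patients affected are also unlikely to be a random subset, because whoever needs steroids at entry probably differs in disease and prognosis. A baseline marker of response could then partly be a marker of steroid use.

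The toxicity correlation has a separate problem. Some toxicities lead to steroids, and steroids change lymphocytes. If a sample taken after onset enters the correlation, cause and effect can be reversed. The two biases can pull in opposite directions: a suppressed baseline makes later counts appear to rise, and steroids on treatment make them appear to fall. The net error therefore has no predictable sign and cannot be corrected afterwards without exposure data. A baseline draw cannot be repeated once treatment has started.

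**Working it through.** The plan states no sample size, precision or effect for CyTOF, so there is no figure to reproduce. The check sets the schedule against the steroid rules and then gives a scale.

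**1. Calendar.** With 28-day cycles, day 15 of cycles 2, 4 and 6 falls on study days 28 + 15 = 43, 84 + 15 = 99 and 140 + 15 = 155. The draws are 56 days apart.

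**2. Baseline.** Steroids are permitted up to day 1 and the draw precedes day 1, so a baseline on steroids is fully compliant. The Table 2 row for concomitant treatment, as extracted, begins after the screening column. A separate screening row covers prior treatment and baseline conditions, but nothing says that it captures steroid dose or date at the draw.

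Let q be the share of patients on steroids at the screening draw and off them later, and s the downward shift that steroids cause in a marker, in SD of the change. With no avelumab effect, the spurious mean rise is q × s. Neither input is in the documents. Assuming q = 10% to 50% and s = 0.5 to 1.0:

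- patients affected: 30 × 0.10 = 3 to 30 × 0.50 = 15
- spurious rise: 0.10 × 0.5 = 0.05 SD to 0.50 × 1.0 = 0.50 SD

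**3. How many patients have a relevant toxicity.** Section 1.2.3 reports potential autoimmune events in 56/480 = 11.7% of solid-tumour patients.

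- expected number: 30 × 56/480 = 3.5, or 35 × 56/480 = 4.1
- chance of at least one: 1 − (1 − 0.1167)^30 = 97.6%, or 98.7% for 35 patients
- if the rate is 5% to 30% (assumption): 1.5 to 9.0 expected of 30

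Not all such events receive steroids, so these are ceilings for a given rate.

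**4. Whether a steroid course covers a draw.** Suppose draws stay on calendar days. A randomly timed course of L days then covers the next draw with probability min(1, L/56). A 30-day course gives 30/56 = 54%; a 44-day course (two weeks before the taper) gives 44/56 = 79%. At 3.5 patients that is 3.5 × 30/56 = 1.9 to 3.5 × 44/56 = 2.8 patients.

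Suppose instead that draws move with delayed dosing. For most steroid-treated events Table 4 resumes avelumab only after the taper, so the next draw would follow the course and coverage by this route would be near zero. The documents do not say which applies.

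Two routes remain either way: corticosteroids for Grade 1 or 2 adrenal insufficiency while avelumab continues (Table 4), and hydrocortisone premedication after some infusion reactions (Table 3). Day 15 is a dosing day, and the timing of the draw relative to premedication is not given.

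**5. Size of a spurious toxicity contrast.** Let c be the share of patients with toxicity who are on steroids at the draw, and π the toxicity rate. With no avelumab effect, the difference between patients with and without toxicity is −c × s. For c = 50% to 100% and s = 0.5 to 1.0 (assumptions) it runs from −0.25 to −1.0 SD. The correlation is −c·s·√(π(1−π)) / √(1 + s²·πc(1−πc)):

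- π = 11.7%, c = 0.5, s = 0.5: −0.25 × 0.321/1.007 = −0.08
- π = 30%, c = 1, s = 1: −1 × 0.458/1.100 = −0.42

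With three or four such patients, one or two samples taken on steroids could decide the contrast.

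**The case against.** The strongest reply is that this is one hypothesis-generating sub-study with no decision attached, and that much of the exposure is avoided or recorded already. Avelumab is usually withheld or stopped while steroids are given, so a draw tied to a cycle day may simply not occur on steroids. Concomitant treatment is recorded during treatment and an adverse event form is completed at each visit, so steroid dates and toxicity onset should be recoverable on treatment. The sample collection and laboratory manuals, which are not part of these documents, may fix draw timing. All of this stands, and it limits the on-treatment half of the point. It does not reach the baseline draw.

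Four stronger readings are tempting and are not supported:

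- **That toxicity and immune change must correlate by construction.** Many toxicities get no steroid course in Table 4, such as Grade 1 diarrhoea, hepatic and renal events, and the section 12.1.3 correlation is with toxicity of any kind. A spurious association can arise; it need not.
- **That at least half of steroid courses will cover a draw.** The 54% holds only if draws keep to the calendar while dosing is delayed.
- **That the first on-treatment sample is always steroid-free.** Section 7.7 and Table 3 permit steroids from the first infusion reaction or adverse event onwards.
- **That on-steroid samples should be dropped from the response analysis.** That would select on an event after treatment start and preferentially remove patients with immune toxicity.

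**Conclusion.** The concern holds in limited form. For any patient on steroids at the screening draw, the schedule as written gives a compromised CyTOF reference, and the plan has no means to identify it. The toxicity correlation is open to reverse causation because no sample is required to precede onset.

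The size cannot be fixed from the documents. Screening steroid use is not stated, the 11.7% comes from solid tumours, and it is unclear whether draws follow the calendar or the dosing. On the stated assumptions, 3 to 15 of 30 baselines could be affected. On treatment, between almost none and about three patients could have a draw on steroids through a treated immune event at the 11.7% rate, and more if the rate is higher. The SD figures rest on an assumed steroid shift of 0.5 to 1.0 SD.

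The outcome is exploratory. The primary, secondary and futility analyses do not use these samples and are unaffected. The change is still worth making because it is cheap and a lost baseline cannot be recovered.

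**What to change.** 1. **Table 2 and section 7.4.2:** move the baseline research blood from screening to cycle 1 day 1, before premedication and infusion, with the safety bloods. Since section 7.3.1 allows safety bloods up to 24 hours before dosing, specify day 1 itself.
2. **Sample form:** record systemic steroid dose and date of last dose at every research draw, with exposure during screening recorded at baseline.
3. **Section 12.1.3, toxicity:** base the main correlation on samples taken before onset of the toxicity concerned. If onset precedes the first on-treatment draw, use the baseline level only, because no change can be computed.
4. **Section 12.1.3, response biomarkers:** keep all samples, flag those taken on steroids, and report a sensitivity analysis stratified by steroid exposure or without the flagged samples.

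The cost is one tube moved to an existing visit, two fields on a form and a few lines of text. Patients registered but never dosed lose their baseline sample, and the pre-onset rule leaves fewer samples for the toxicity correlation. Moving the draw reduces carry-over from recently stopped steroids but may not remove it, which is why the exposure record is needed as well. No rule on steroid treatment changes.

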12.2 Analysis of Outcome Measures

Primary Outcome Measures

- Best overall response rate (PR + CR) during 8 cycles of treatment will be presented as the number and proportion of patients achieving a response over the total number of patients registered to the trial. Patients who die due to disease or toxicity during the first 8 cycles of treatment and patients who are not assessable will be classed as non-responders.

Posterior probability plots will also be produced together with the probability that the true effect is greater than 35%.

Secondary Outcome Measures

- Toxicity - The number and proportion of patients who experience one or more grade 3 or 4 adverse event or serious adverse event of any grade will be reported over the total number patients in the trial

- Time to event outcomes will be estimated using Kaplan Meier method. Point estimates will be presented at 6 and 12 months with 95% confidence intervals.
- Reduction in tumour size measured as maximum percentage change in the radiological sum of the product of the diameters from baseline will be presented as a mean and standard deviation or medians with an interquartile range depending on the distribution of the data.

Exploratory outcome measures

- Percentage of PD-L1 expression will be analyses at the Leicester Cancer Centre
- Cell free DNA levels and disease status correlation will be performed by the Leicester Cancer Centre
- Multicolour peripheral blood immunophenotyping will be performed by the Leicester Cancer Centre
- CyTOF study: biomarkers of response data will be acquired via mass flow cytometry at the Leicester Cancer Centre

All summaries and statistical analyses will be performed on an intention-to-treat (ITT) population including patients who are ineligible or non-compliant and a per protocol population of only patients who were eligible and received at least 1 dose of treatment.

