6. TRIAL ENTRY

Patients will be registered to the trial via the Cancer Research UK Clinical Trials Unit (CRCTU) by phone or using the CRCTU systems portal. An eligibility checklist and registration form (found in the ISF) should be completed prior to registration by the Investigator or designee.

Registration via CRCTU systems portal:

<https://www.cancertrials.bham.ac.uk/AvailTLive>

Login details will be provided by the trials office as part of site initiation. The patient trial number will be provided by the online system. A report can be printed as confirmation.

Registration via [contact]

9am-5pm Monday to Friday

The patient trial number will be given over the telephone, followed by a fax confirmation.

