7. TREATMENT DETAILS

7.1 Trial Treatment

All patients registered to the trial will receive avelumab at the dose of 10 mg/kg by intravenous (IV) infusion once every 2 weeks for 8 cycles (28 day cycles). Each infusion of avelumab should be delivered over 1h (-10/+20min) unless IRR is experienced (see Table 3). Avelumab dose should be prepared in accordance with the NHS England National Dose Banding Table for avelumab (please refer to the pharmacy manual)

All patients should be weighed within 3 days prior to day 1 dosing for every cycle to ensure they did not experience either a weight loss or gain >10% from the weight used for the last dose calculation. For weight change less than 10% the decision to recalculate the avelumab dose can be in accordance with institutional practice. If the patient experienced either a weight loss or gain >10% compared to the weight used for the last dose calculation, the amount of study drug must be recalculated.

Premedication

Premedication with an antihistamine and with paracetamol, to mitigate IRRs and is **mandatory** approximately 30 to 60 minutes prior to the first four doses of avelumab (Cycles 1-2), but may continue to be administered for subsequent cycles based upon clinical judgment and presence/severity of prior infusion reactions, at the treating Investigator's discretion. For example, 25-50 mg diphenhydramine and 500-650 mg paracetamol IV or oral equivalent should be considered.

This regimen may be modified based on local treatment standards and guidelines as appropriate provided it does not include systemic corticosteroids.

Avelumab should be administered in a setting that allows for immediate access to an intensive care unit or equivalent environment and administration of therapy for anaphylaxis, such as the ability to implement immediate resuscitation measures. Steroids (dexamethasone 10 mg), epinephrine (1:1,000 dilution), allergy medications (IV antihistamines), bronchodilators, or equivalents, and oxygen should be available for immediate access.

Following avelumab infusions, patients must be observed for 2 hours post-infusion for potential IRRs.

Patients will be assessed during the course of treatment, at progression or after completion of 8 cycles of treatment as described in section 7.3.

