8.1.3 Reporting period

Details of all AEs (except those listed above) will be documented and reported from the date of commencement of protocol defined treatment until 30 days after the administration of the last treatment.

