8.2.5 Data/Safety Committee

The independent Trial Safety Committee (TSC) will review all SAEs.

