12.1.2 Secondary outcome measures

- Toxicity assessed using CTCAE v4.0 will be defined as the number and proportion of patients who experience one or more grade 3 or 4 adverse event or serious adverse event of any grade
- Best overall response (Partial Remission (PR) + Complete Response (CR)) at any time of treatment will be assessed using contrast-enhanced CT scans of the neck, chest, abdomen and pelvis, using the Revised Response Criteria for Malignant Lymphoma (²⁷)
- Maximum percentage change in the sum of the product of diameters (SPD) of target tumour masses assessed by contrast-enhanced CT scans of the neck, chest, abdomen and pelvis, using the Revised Response Criteria for Malignant Lymphoma²⁷
- Duration of response is defined as the time from first documented response until relapse/progression, as determined by the Revised Response Criteria²⁷, or death. Patients who are relapse/progression free and alive will be censored at date last seen.
- Progression free survival is defined as the time from date of registration to the date of disease progression or date of death from any cause. Patients not reaching progression or death at the time of analysis will be censored at the last date they were known to be alive and progression free. Patients will be followed up for a minimum of 12 months.
- Overall survival time is defined as the time from date of registration to the date of death from any cause. Patients discontinuing the study, lost to follow-up or still alive at the end of the study will be censored at the date of last follow-up. Patients will be followed up for a minimum of 12 months.

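### Section 12.2 reports toxicity over all patients in the trial rather than all dosed patients: a minor denominator point that is cheap to correct

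*Combined protocol and SAP*

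**What the plan says.** Section 12.1.2 names the toxicity outcome but no denominator: it "will be defined as the number and proportion of patients who experience one or more grade 3 or 4 adverse event" or a serious adverse event. The denominator comes in section 12.2: "serious adverse event of any grade will be reported over the total number patients in the trial".

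The closing sentence of 12.2 then puts all summaries, toxicity included, on two populations. The first is "an intention-to-treat (ITT) population including patients who are ineligible or non-compliant"; it has no dosing condition. The second is "a per protocol population of only patients who were eligible and received at least 1 dose of treatment"; it has one, but also requires eligibility. No population of all dosed patients is defined anywhere in the document.

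Three other sections bear on the point:

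- Section 8.1.3 has adverse events reported "from the date of commencement of protocol defined treatment until 30 days after the administration of the last treatment".
- Section 7.1 states the intention: "All patients registered to the trial will receive avelumab".
- Section 6 puts an eligibility check before entry: "An eligibility checklist and registration form (found in the ISF) should be completed prior to registration by the Investigator or designee".

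On a related matter, the period for collecting adverse events is given in two ways. Table 2 (section 7.3) runs it to 28 days after treatment discontinuation. Sections 8.1.3 and 7.9 run it to 30 days after the last treatment or dose, and only 7.9 adds a tolerance of ± 5 days.

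**The concern.** The natural denominator for a toxicity rate is the set of patients exposed to the drug. Neither planned population is sure to be that set. ITT can contain patients who were never dosed; they count below the line and can never count above it, so any error is downward. Per protocol leaves out treated patients who prove ineligible, together with any events they had, so its error can go either way.

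A registered patient who is never dosed is plausible, though not planned. Section 5.1 allows screening tests up to 28 days before registration, and section 7.2 requires blood counts and liver and renal criteria to be checked again within 24 hours of each dose, the first included. The definitions in 12.2 themselves allow for ineligible patients and for patients without a dose.

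What is at stake is the clarity of one secondary, descriptive result. Section 1.2.2 assumes that the safety profile seen in solid tumours carries over to haematological malignancy. The avelumab experience cited in section 1.2.3 is in patients who were treated, so a rate diluted by untreated patients would not share that denominator.

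**Working it through.** **Plan's own figure.** The document states no expected toxicity rate, so there is nothing to reproduce on this outcome. The posterior probabilities behind the sample size concern response and do not depend on this point.

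**Inputs.** N = 30, up to 35 (section 3). Let u be the number registered but never dosed, k the number treated but ineligible, x the number of patients with a qualifying event, and e the number of those x who are among the k ineligible. The documents give none of u, k, x or e; every value below is an assumption. N is taken as all registered patients. That is an inference: the primary outcome in the same section is reported over registered patients, while the toxicity line is worded more loosely.

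**Formulas.** Because events are reported only from first treatment, all x patients were dosed.

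- All treated: x / (N − u)
- ITT: x / N = all-treated rate × (1 − u/N)
- Per protocol: (x − e) / (N − u − k)

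ITT equals the all-treated rate if u = 0. Per protocol equals it if k = 0, whatever u is.

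**ITT against all treated.** With all-treated rate p, the loss is p × u/N. At N = 30, in percentage points:

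| Assumed p | u = 0 | u = 1 | u = 2 | u = 3 |
|---|---|---|---|---|
| 20% | 0 | 0.7 | 1.3 | 2.0 |
| 40% | 0 | 1.3 | 2.7 | 4.0 |
| 60% | 0 | 2.0 | 4.0 | 6.0 |

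For example, 40% × 3/30 = 4.0 points, so ITT shows 36.0%. At N = 35 and p = 40% the loss is 40% × 1/35 = 1.1 points at u = 1 and 40% × 3/35 = 3.4 at u = 3. If k = 0 in any of these cases, the per-protocol summary still shows p.

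**Both conditions fail.** Take N = 30 and x = 12.

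- u = 1, k = 1: all treated 12/29 = 41.4%; ITT 12/30 = 40.0% (1.4 low); per protocol 11/28 = 39.3% (2.1 low) if the ineligible patient had an event, or 12/28 = 42.9% (1.5 high) if not.
- u = 2, k = 2: all treated 12/28 = 42.9%; ITT 40.0% (2.9 low); per protocol 10/26 = 38.5%, 11/26 = 42.3% or 12/26 = 46.2%, that is, from 4.4 low to 3.3 high.

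**Scale.** The exact (Clopper–Pearson) 95% interval for 12/28 is 24.5% to 62.8%, which is 18.4 points below and 19.9 above the estimate. Every shift shown is well inside that.

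**The case against.** The strongest reply is that nothing is wrong if the trial runs as written. If every registered patient is dosed, as section 7.1 plans, ITT is the all-treated set and the effect is nil. If some are not dosed, the plan already offers a dosed-only summary through per protocol, which is exact unless an ineligible patient was treated, and the eligibility checklist should make that rare. Nor is information lost. Section 12.2 reports the number of affected patients as well as the proportion, and every dosed patient is in ITT, so anyone told how many were dosed can recover the all-treated rate exactly.

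All of this stands, and it is why the point is minor. What remains is that the plan does not commit to stating the number dosed, and that no summary is guaranteed to have exposed patients as its denominator.

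The reading of the denominator as all registered patients can also be challenged, since ITT is described by whom it includes and not by registration. That is fair. But if the sponsor means something else, the same sentence needs the same clarification.

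**Conclusion.** The point holds as a minor improvement to an analysis choice. On the all-registered reading, each undosed patient lowers the ITT toxicity rate by the fraction 1/N of the all-treated rate. That is about 1.3 points per undosed patient at an assumed 40% and N = 30, and zero if none is undosed. Per protocol covers this gap unless an ineligible patient was treated.

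Three stronger inferences are not supported:

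- A reader might infer that the trial will understate toxicity materially. The documents give no count of undosed patients and plan for none.
- A reader might try to put a probability on both populations missing the all-treated rate. That needs per-patient risks of going undosed and of being treated while ineligible, and the documents supply neither.
- A reader might infer that safety oversight is weakened. Section 12 attaches no threshold to this proportion. Section 12.3 lets the committee weigh all outcomes but sets a number only for response. Committee review does not run through this denominator: "The independent Trial Safety Committee (TSC) will review all SAEs", and section 13.4 has it monitor all safety data.

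The adverse-event window is a separate, small consistency point. The 2-day difference between Table 2 and section 7.9 falls within the tolerance in 7.9, but 8.1.3 has no tolerance, and the start points are worded differently. A larger gap cannot be inferred, because no section says how discontinuation is dated for this purpose; section 7.8 times the End of Treatment visit from the last dose.

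**What to change.** In section 12.2, make the main toxicity denominator all patients who received at least one dose of avelumab, regardless of eligibility, and report the number registered but never dosed. Amend the closing sentence of 12.2 so that ITT and per-protocol toxicity are supplementary to that summary. This takes two wording edits. It needs no extra patients or visits, and no new data, because the case report form already captures treatment details (section 9.1). The one downside is that the reported toxicity rate may be slightly higher than under the present wording.

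Separately, reconcile Table 2 with sections 8.1.3 and 7.9 so that the adverse-event period has one length, one start point and one stated tolerance throughout.
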